#### 14.1.24 Time to response

**Time to overall response (CR or PR)** is the time between date of randomization/start of treatment until first documented response (CR or PR). The response may need to be confirmed depending on the type of study and its importance. Where the response needs to be confirmed then time to response is the time to the first CR or PR observed.

Although an analysis on the full population is preferred a descriptive analysis may be performed on the “responders” subset only, in which case the results should be interpreted with caution and in the context of the overall response rates, since the same kind of selection bias may be introduced as described for duration of response in [Section 14.1.23](#). It is recommended that an analysis of all patients (both responders and non-responders) be performed whether or not a “responders only” descriptive analysis is presented. Where an inferential statistical comparison is required, then all patients should definitely be included in the analysis to ensure the statistical test is valid. For analysis including all patients, patients who did not achieve a response (which may have to be a confirmed response) will be censored using one of the following options.

- at maximum follow-up (i.e. FPFV to LPLV used for the analysis) for patients who had a PFS event (i.e. progressed or died due to any cause). In this case the PFS event is the worst possible outcome as it means the patient cannot subsequently respond. Since the statistical analysis usually makes use of the ranking of times to response it is sufficient to assign the worst possible censoring time which could be observed in the study which is equal to the maximum follow-up time (i.e. time from FPFV to LPLV)
- at last adequate tumor assessment date otherwise. In this case patients have not yet progressed so they theoretically still have a chance of responding

**Time to overall complete response (CR)** is the time between dates of randomization/start of treatment until first documented CR. Similar analysis considerations including (if appropriate) censoring rules apply for this endpoint described for the time to overall response endpoint.

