- The updated analyses for **all MET mutant patients** (Cohorts 4, 5b and 6, and 7) will be conducted when Last Patient Last Visit is reached.
- Data from cohorts (Cohort 1-7) will be included for patient disposition, baseline characteristics and safety analyses. Patient disposition, baseline characteristics and safety analyses will also be presented combining the MET mutant patients (pre-treated, treatment-naïve and all MET mutant patients) and all amplified patients (complementary subgroup to MET mutant patients).
- Data from MET mutant cohorts (Cohort 4, 5b, 6 and 7) will be included for efficacy a [REDACTED] They will also presented combining the MET mutant patients (pre-treated and treatment-naïve MET mutant patients).
- No PK analyses will be included in this report as no additional PK samples are analyzed at this time.

[REDACTED]

All available data from all patients will be summarized in the final Clinical Study Report (CSR).

[Section 4.1](#) provides further details regarding data to be included in the analyses.

General presentation of descriptive summaries

Qualitative data (e.g., gender, race) will be summarized by frequency counts and percentages. Percentages will be calculated using the number of patients in the relevant population or subgroup as the denominator.

Continuous data (e.g., age, body weight) will be summarized by appropriate descriptive statistics (i.e. mean, standard deviation, median, minimum, and maximum).

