2.7.1 Variable

The primary variable used to evaluate the anti-tumor activity of INC280 is the overall response rate (ORR), defined as the proportion of patients with a best overall response (BOR) as complete response (CR) or partial response (PR), as assessed per RECIST 1.1 by BIRC.

Best overall response (BOR)

The BOR will be assessed based on reported lesion responses at different evaluation time points. Both CR and PR must be confirmed by repeat assessments performed not less than 4 weeks after the criteria for response are first met. The next scheduled assessment may be used for purposes of confirmation of response.

BOR for each patient is determined from the sequence of overall (lesion) responses according to the following rules:

- CR = at least two determinations of CR at least 4 weeks apart before progression
- PR = at least two determinations of PR or better at least 4 weeks apart before progression (and not qualifying for a CR)
- SD = at least one SD assessment (or better) > 6 weeks after start of study drug (and not qualifying for CR or PR).
- PD = progression ≤ 12 weeks after start of study drug (and not qualifying for CR, PR or SD).
- UNK = all other cases (i.e. not qualifying for confirmed CR or PR and without SD after more than 6 weeks or progression within the first 12 weeks)

Only tumor assessments performed before the start of any further anti-neoplastic therapies (i.e. any additional secondary anti-neoplastic therapy or anti-cancer surgery) and within 30 days after the last dose of study treatment will be considered in the assessment of BOR.

Local bone radiotherapy for analgesic purposes or for lytic lesions at risk of fracture are not considered secondary anti-neoplastic therapy. If a patient receives any further anti-neoplastic therapy while on study, any subsequent assessments will be excluded from the BOR determination. Further anti-neoplastic therapies will be identified via protocol deviations or from the data collected on 'Anti-neoplastic therapies since last date of study drug' as appropriate. Palliative radiotherapy in the bone is the only setting of radiotherapy allowed during the study. Therefore palliative radiotherapy in the bone will not be considered as an anti-neoplastic therapy for assessment of BOR.

Clinical deterioration will not be considered as documented disease progression.

Patients with BOR 'unknown' will be summarized by reason for having unknown status. The following reasons will be used:

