2.7.3 Handling of missing values/censoring/discontinuations

Confirmed PR or CR reported prior to any additional anticancer therapy will be considered as responses in the calculation of the ORR irrespective of the number of missed assessments before response.

Patients with a BOR of 'Unknown' per RECIST 1.1 will be considered as non-responders when estimating ORR.

Patients with no BIRC data will be considered as non-responders when estimating ORR.

Patients who have disease progression and continue to receive study drug after progression will qualify for PD at the time of progression and will be counted as PD in the derivation of ORR and any other efficacy endpoints.

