DOR will be described in tabular and graphical format using Kaplan-Meier methods by cohort. The Kaplan-Meier estimate of the distribution function will be constructed. Kaplan-Meier curves will be constructed. The number of patients at risk at certain time points will be shown on the plot. The estimated median (in months) along with 95% CIs, as well as 25th and 75th percentiles will be reported ([Brookmeyer and Crowley 1982](#)). In addition, Kaplan-Meier estimated probabilities with corresponding 95% CIs at several time points (including at least 3, 6, 9, 12 and 18 months) will be summarized by cohort. These analyses will be performed

separately based on BIRC assessment and based on investigator assessment. Refer to [Section 4.6.3](#) for further details regarding derivation of Kaplan-Meier estimates.

Disease control rate (DCR)

DCR is defined as the proportion of patients with best overall response of CR, PR, or SD per RECIST 1.1. DCR will be estimated and the binomial exact 95% CI will be provided by cohort. These analyses will be performed separately based on BIRC assessment and based on investigator assessment.

Time to response (TTR)

TTR is defined as the time from start of study drug to first documented response (CR or PR, which must be confirmed subsequently) for patients who achieved a confirmed PR or CR. All patients in the FAS will be included in time to response calculations. Patients who did not achieve a confirmed PR or CR, will be censored at:

- the maximum follow-up time (i.e. first patient first treatment to last patient last treatment by cohort used for the analysis) for patients who had a PFS event (i.e. either progressed or died due to any cause), or at the date of last adequate tumor assessment date otherwise.

TTR will be summarized in 6-weeks intervals using descriptive statistics. The distribution of time to response will be estimated using the Kaplan-Meier method and the median time to response will be presented along with 95% confidence interval only if a sufficient number of responses is observed. Failure curves (ascending Kaplan-Meier curves) will be constructed. These analyses will be performed separately based on BIRC assessment and based on investigator assessment.

Progression-free survival (PFS)

PFS is defined as the time from the start date of study drug to the date of the first radiologically documented PD or death due to any cause.

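### In the last-visit report, the all-patient time-to-response curve can end above the ORR, because some final non-responders are censored as if they might still respond

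*SAP*

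**What the plan says.** **Population and display (SAP 2.8.1, Time to response).** "All patients in the FAS will be included in time to response calculations". "Failure curves (ascending Kaplan-Meier curves) will be constructed", for BIRC and investigator assessment separately. A median is printed only if there are enough responses.

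**Censoring of patients without a confirmed response (same section).** Maximum follow-up, by cohort, applies "for patients who had a PFS event (i.e. either progressed or died due to any cause"; everyone else is censored "or at the date of last adequate tumor assessment date otherwise".

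**Reason for the split (protocol 14.1.24).** A PFS event means that the patient cannot respond later. Of the others the protocol says: "In this case patients have not yet progressed so they theoretically still have a chance of responding".

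**When a response can still count (SAP 2.7.1).** Only scans before any further anti-neoplastic therapy and "within 30 days after the last dose of study treatment will be considered in the assessment of BOR".

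**How ORR treats the unresolved cases (SAP 2.7.3).** An unknown best overall response (BOR) counts as non-response, and "Patients with no BIRC data will be considered as non-responders when estimating ORR".

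**Timing (SAP 2.1).** The updated analysis of the MET mutant cohorts (4, 5b, 6 and 7) "will be conducted when Last Patient Last Visit is reached".

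**Protocol 10.5.2** defines TTR for confirmed responders only and plans a descriptive summary in 6-week intervals. The SAP adds the all-patient curve.

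**The concern.** The plan's own test for holding a non-responder in the risk set is whether a response is still possible. A PFS event is one way for that possibility to end. SAP 2.7.1 supplies others: new anti-neoplastic therapy, or more than 30 days since last dose. Withdrawal, loss to follow-up and absence of BIRC data end it too. In an ongoing study the last-scan rule suits patients who are still being treated. At last patient last visit it also catches patients whose BOR is already closed.

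The clearest case is a patient with no BIRC data who has not died. SAP 2.7.3 counts this patient as a non-responder in the ORR denominator. SAP 2.8.1 censors the patient for BIRC PFS at the start of study drug, so there is no PFS event. Protocol 14.1.25 sets the last adequate assessment to the start of treatment when there is no post-baseline assessment. The patient therefore leaves the TTR risk set on day 1, and Kaplan-Meier treats the patient as having the same chance of responding as those who remain.

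At stake is one secondary display. A reader will compare the end of the response curve with the ORR in the same report. The two should agree once response status is final, and any disagreement from this source makes the curve look better.

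**Working it through.** **1. Reproduce the figure that the curve would be compared with.** The documents give no TTR curve value. Protocol 1.2.1.2.2 gives BIRC ORR at the 09-Aug-2018 cut-off. Responder counts follow from rate times n: 0.391 × 69 = 27 and 0.720 × 25 = 18.
- Cohort 4: 27/69 = 39.1%, Clopper-Pearson 95% CI 27.6 to 51.6. Matches.
- Sub-cohort 5b: 18/25 = 72.0%, CI 50.6 to 87.9. Matches.

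These interim counts serve only as an example below.

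**2. Bounds on the end of the curve.** Let R be confirmed responders, N all patients, and m non-responders whose BOR window has closed without a PFS event. Hold all other non-responders at maximum follow-up.
- If all m are censored at or after the last first response, nobody leaves the risk set early and 1 - KM ends at R/N, the ORR.
- If all m are censored before the first response, they drop out of every risk set and 1 - KM ends at R/(N-m).
- Otherwise the end lies between the two. It cannot lie below the ORR.

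Maximum excess = R/(N-m) - R/N.

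**3. Numbers.** Neither m nor the scan dates are in the documents. Assumed: first responses split about 60/20/10/10% over weeks 6, 12, 18 and 36, and all m censored together at the time shown, with events before censoring at ties.

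For Cohort 4 the split is 16, 5, 3 and 3 responders. With m = 5:
- day 1: 27/64 = 42.2%
- week 6: 1 - (53/69)(37/48) = 40.8%
- week 12: 1 - (48/69)(37/43) = 40.1%
- week 36 or later: 1 - 42/69 = 39.1%

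| Example | m | Censored day 1 | Week 6 | Week 12 | Week 36 or later |
|---|---|---|---|---|---|
| Cohort 4, ORR 39.1% | 1 | 39.7% | 39.4% | 39.3% | 39.1% |
| Cohort 4 | 5 | 42.2% | 40.8% | 40.1% | 39.1% |
| Cohort 4 | 10 | 45.8% | 42.8% | 41.4% | 39.1% |
| Sub-cohort 5b, ORR 72.0% | 3 | 81.8% | 79.6% | 77.1% | 72.0% |

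The day 1 column is the upper bound R/(N-m): 27/68, 27/64, 27/59 and 18/22.

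**4. After the fix.** If every non-responder is final and held at maximum follow-up, the curve ends at exactly 39.1% and 72.0%.

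**The case against.** The case against is substantial and narrows the point in several ways.

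- **The excess is not automatic.** A reader might infer that the curve must end above the ORR. It does so only if at least one such patient's last adequate scan precedes another patient's first response. Stable-disease patients followed past the last first response add nothing. This stands.
- **Many patients who stop drug are already handled.** A reader might infer that toxicity stops and patients on new therapy are generally affected. After stopping for reasons other than progression, scans continue until BIRC-confirmed PD (protocol 4.1.4 and 7.1.5.2). SAP Table 2-1 ignores new therapy for PFS and counts death from any cause. Most who are followed would reach a PFS event and be held at maximum follow-up. What remains is mainly withdrawals, losses, patients with no BIRC data, and event-free patients. This stands.
- **Events after two or more missed scans.** Table 2-1 situation C2 censors these for PFS, so a reader might infer that they are censored early for TTR. The SAP's gloss, progressed or died from any cause, reads literally as including them in the maximum follow-up group. The text is ambiguous and should be settled.
- **BOR may not be final for everyone.** Protocol 4.3 allows the study to end by transfer to another study or to commercial supply. Patients still on drug without PD could still respond, and for them the present rule is right. Their number is not given.
- **The median.** A reader might infer that the reported median TTR is shortened. In the Cohort 4 example the curve reaches 50% only if 15 of 69 patients leave on day 1 (27/54 = 50.0%). In a cohort with ORR above 50%, any shift depends on dates that the documents do not give. No effect is shown.
- **It is the protocol's own option, for a secondary endpoint without a hypothesis.** Also true. But the protocol justifies that option by the chance of a later response, and for these patients the chance has gone. Extending the plan's existing treatment of patients who cannot respond is therefore more than a preference.

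**Conclusion.** The inconsistency is real and minor. At last patient last visit, SAP 2.8.1 censors some patients as possible future responders whom SAP 2.7.1 and 2.7.3 have already fixed as non-responders. The error can only push the TTR curve up, by between 0 and R/(N-m) - R/N. In the Cohort 4 example with m = 5 that is 0 to 3.1 points (42.2 - 39.1). In a small cohort it can be larger: 0 to 9.8 points in the 5b example with m = 3 (81.8 - 72.0).

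These sizes rest on assumed m, and the values between the bounds also on assumed response and censoring times. The true excess is unknown and may be small. The primary ORR, its exact interval and the descriptive TTR among responders are not affected.

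**What to change.** In SAP 2.8.1, replace the last-scan clause with three statements:

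1. Every patient without a confirmed response whose BOR window has closed is censored at the cohort's maximum follow-up. The window closes with a PFS event, new anti-neoplastic therapy, more than 30 days since last dose, withdrawal or loss to follow-up, or absence of BIRC data (for the BIRC analysis).
2. Censoring at the last adequate assessment applies only to patients who, at the cut-off, are still on treatment without PD or still within the BOR window.
3. Patients with PD or death after two or more missed assessments (Table 2-1, situation C2) are also held at maximum follow-up for TTR.

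The cost is a short change to the SAP text and a small programming change. The secondary TTR curve becomes slightly less favourable. It will end at the ORR whenever BOR is final for all patients in the cohort.

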2.8 Analysis of secondary variables

2.8.1 Efficacy

All secondary endpoint analyses will be performed based on the FAS, unless otherwise specified. Efficacy will also be presented combining the MET mutant cohorts per line of treatment as defined in [Section 2.2](#).

No adjustment for multiple testing will be made.

Key secondary efficacy endpoints

The key secondary objective is to evaluate duration of response (DOR) as assessed by BIRC, by cohort.

Among patients with a confirmed response (PR or CR), DOR is defined as the time from first documented response (PR or CR) to the date of first documented PD or death due to any cause. If a patient has not had an event, DOR is censored at the date of last adequate tumor assessment.

The censoring and event date options to be considered for the main analysis are presented in [Table 2-1](#).

Table 2-1 Outcome and event dates for DOR and PFS analyses

Situation	Date	Outcome
A No baseline assessment	Date of first dose of study drug ^a	Censored
B Progression at or before next scheduled Assessment	Date of progression	Progressed
C1 Progression or death after exactly one missing assessment	Date of progression (or death)	Progressed
C2 Progression or death after two or more missing assessments	Date of last adequate assessment	Censored
D No progression	Date of last adequate assessment	Censored
E Treatment discontinuation due to 'Disease progression' without documented progression, i.e. clinical progression based on investigator claim	N/A	Information ignored. Outcome derived based on radiology data only.
F New anticancer therapy given	Ignore the new anticancer therapy and follow situations above	As per above situations
G Deaths due to reason other than deterioration of 'Study indication'	Date of death	Progressed

^a The rare exception to this is if the patient dies no later than the time of the second scheduled assessment as defined in the protocol in which case this is a PFS event at the date of death

DOR will be described in tabular and graphical format using Kaplan-Meier methods. The Kaplan-Meier estimate of the distribution function will be constructed. Kaplan-Meier curves

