If a patient has not progressed or is not known to have died at the date of analysis cut-off, PFS will be censored at the date of the last adequate tumor evaluation before the cut-off date. PFS events documented after the initiation of new anti-neoplastic therapy (i.e. RECIST 1.1 documented disease progression or death) will be considered for the primary analysis provided tumor assessments continue after initiation of the new cancer therapy. Clinical deterioration will not be considered as a qualifying event for progression. Refer to [Table 2-1](#) for censoring and event date options and outcomes for PFS.

In particular, PFS will be censored at the last adequate tumor assessment if one of the following occurs: absence of event; the event occurred after two or more missing tumor assessments (see [Section 4.6.1](#)). See also [Section 4.6.1](#) describing the special case of a missing baseline tumor assessment.

Patients with no BIRC data will be considered censored at the start date of study drug.

PFS will be described in tabular and graphical format using Kaplan-Meier methods as described for DOR by cohort, including estimated median (in months) with 95% CI, 25th and 75th percentiles and Kaplan-Meier estimated probabilities with corresponding 95% CIs at several

time points. Censoring reasons will also be summarized by cohort. These analyses will be performed separately based on BIRC assessment and based on investigator assessment.

In addition, PFS table will be repeated on the PPS.

Overall survival (OS)

OS is defined as the time from the start date of study drug to the date of death due to any cause. If the patient is alive at the date of the analysis cut-off or lost to follow-up, then OS will be censored at the last contact date prior to data cutoff date (see [Section 4.3](#) for further details on derivation of last contact date).

OS will be described in tabular and graphical format using Kaplan-Meier methods as described for DOR by cohort, including estimated median (in months) with 95% CI, 25th and 75th percentiles and Kaplan-Meier estimated probabilities with corresponding 95% CIs at several time points. Censoring reasons will also be summarized by cohort.

OS from initial diagnosis to the date of death due to any cause will also be analyzed. Date of censoring is the same as defined for OS analysis.

Duration of Follow-up

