As detailed in Section 14 (Appendix II) of the CINC280A2201 protocol, the PFS censoring and event date options depend on the presence and the number of missing tumor assessments. *For example, an event occurring after two or more missing assessments is censored in the analysis of PFS at the last adequate tumor assessment before the event date.*

An exact rule to determine whether there is none, one or two missing assessments is therefore needed. This rule will be based on the distance between the last adequate tumor assessment date and the event date.

If the distance is larger than threshold D_1 or D_2 then the analysis will assume one or two missing assessments, respectively. The threshold D_1 will be defined as the protocol specified interval between the tumor assessments plus the protocol allowed window around the assessments. Similarly, the threshold D_2 is defined as two times the protocol specified interval between the tumor assessments plus the protocol allowed window around the assessments. In this study, the protocol defined schedule of tumor assessment is every 6 weeks and each assessment is expected to be performed at the scheduled time point plus or minus 1 week, i.e. the window is 2 weeks, then any distance larger than $D_1 = 6+2 = 8$ weeks means one missing assessment and any distance larger than $D_2 = (2*6) + 2 = 14$ weeks means two missing assessments.

The same definition of D_2 will be used to determine the PFS censoring reason.

Possible censoring reasons for PFS are:

- 1: Ongoing without event
- 2: Lost to follow-up
- 3: Withdraw consent
- 4: Adequate assessment no longer available

5: New cancer therapy added

6: Event after ≥ 2 missing tumor assessments

PFS censoring reason is then derived by the following sequence of rules.

- If patient is considered to have a PFS event then PFS censoring reason is set to missing.
- Else if patient has had no baseline assessment then PFS censoring reason = 4.
- Else if patient has a PFS event after two or more missing assessments [If (PFS Event date \leq Censoring date and (PFS Event date - Date of last adequate tumor assessment (LATA) \geq D2)] then PFS censoring reason =6:
- Else if patient has no PFS event, and patient is censored at a date after two or more missing assessments ((Censoring date - Date of LATA) \geq D2) then PFS censoring reason = 4
- Else if censoring date equals the start date of further anti-neoplastic therapy then PFS censoring reason = 5

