- Else if censoring date equals date of discontinuation due to consent withdrawal then PFS censoring reason = 3
- Else if censoring date equals date of discontinuation due to loss to follow-up then PFS censoring reason = 2
- Else if the censoring date equal the analysis cut-off date and the time between LATA and the cut-off is greater than D2 days then PFS censoring reason = 4
- Else if the censoring date equal the analysis cut-off date and the time between LATA and the cut-off is less than or equal to D2 days then PFS censoring reason = 1

Where censoring date = minimum(analysis cut-off date, start date of further anti-neoplastic therapy, date of discontinuation due to consent withdrawal, date of discontinuation due to loss to follow-up).

Non-measurable disease at baseline

As specified in Section 14 (Appendix II) of the CINC280A2201 protocol, the RECIST 1.1 criteria imply that only patients with measurable disease at baseline should be included in the study. If a patient without measurable disease is enrolled, the intent-to-treat (ITT) principle requires including these patients in the analyses. Hence, analyses will be based on FAS including patients with either measurable or non-measurable disease. Therefore, a rule needs to be specified on how to handle these cases.

As specified in Table 3-1 of Section 14 (Appendix II) of the CINC280A2201 protocol, overall lesion response can be derived for patients without measurable disease at baseline as follows ([Table 4-3](#)).

Table 4-3**Overall lesion response at each assessment: patients with non-target disease only**

Non-target lesions	New Lesions	Overall lesion response
CR	No	CR
Non-CR/Non-PD ¹	No	Non-CR/non-PD
UNK	No	UNK
PD	Yes or No	PD
Any	Yes	PD

¹ In general, the **non-CR/non-PD response** for these patients is considered equivalent to an SD response in endpoint determination.

Missing baseline tumor assessment

As specified in Section 14 (Appendix II) of the protocol, since the timing of PD cannot be determined for patients with missing baseline tumor assessment, these patients are censored in the PFS analysis at the start date of treatment. This rule, however, only applies to the ‘PD component’ of the PFS or DOR assessment.

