Patients without baseline tumor assessment who die within D₂ distance from start date of treatment will be counted as having an event in the primary analysis of PFS. All deaths will be counted in the OS analysis regardless of presence or absence of the baseline tumor assessment.

Construction of waterfall graphs

The waterfall graphs will be used to depict the anti-tumor activity. These plots will display the best percentage change from baseline in the sum of the measured diameter of all target lesions based on the on-treatment assessments occurring prior to the first PD for each patient with measureable disease at baseline. The proportions of patients with various degrees of tumor shrinkage or growth can then represent a useful efficacy metric.

However, caution needs to be paid to the assessments, where an occurrence of a new lesion or worsening in non-target lesions (resulting in PD as an overall lesion response at given assessment) contradicts the measurements obtained on target lesions. These assessments will not be displayed as bars in the graph. If such a “contradicting” assessment represents the only post-baseline assessment for a patient, then the patient will be represented by a special symbol (e.g. *) in the waterfall graph.

The assessments with unknown target response and also assessments with unknown overall response will be excluded. Patients without any valid assessments will be completely excluded from the graphs.

The total number of patients displayed in the graph needs to be shown and this number will be used as a denominator when calculating the percentages of patients with tumor shrinkage and tumor growth. Footnote will explain the reason for excluding some patients (due to absence of any valid assessment).

Patient who have discontinued will be represented by a special symbol in the waterfall graph.

All possible assessment scenarios are described in [Table 4-4](#).

Table 4-4 Inclusion/exclusion of assessments used in waterfall graph

Criteria for inclusion/exclusion			Possible source of contradictions	
Target response	Overall lesion response	Include in waterfall	Non-target response	New lesion?
CR/PR/SD	PD	Yes but as * only	PD	any
CR/PR/SD	PD	Yes but as * only	Any	Yes
UNK	UNK or PD	No	Any	any
CR/PR/SD	UNK	No	UNK	No
CR/PR/SD	CR/PR/SD	Yes as a bar	SD/IR	No
PD	PD	Yes as a bar	Any	any

The following algorithm will be used to construct the graph:

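### SAP 2.8.1 censors patients with no BIRC data on day 1 for PFS with no exception for death, against the plan's own early-death rule

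*SAP*

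**What the plan says.** SAP 2.8.1 runs PFS from first dose "to the date of the first radiologically documented PD or death due to any cause". Protocol 10.5.2 has the same event definition and names two grounds for censoring: no event, and an event after two or more missing tumor assessments. Missing central reads are not among them, and SAP section 3 declares no change to the protocol-specified analyses.

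Later in the same SAP text comes the rule at issue: "Patients with no BIRC data will be considered censored at the start date of study drug". The sentence before it points to SAP 4.6.1 for missing baselines, but the rule is not made subject to that section.

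The plan handles a missing baseline assessment in two other places:

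- Table 2-1, situation A, censors at first dose, but its footnote adds: "The rare exception to this is if the patient dies no later than the time of the second scheduled assessment". In that case the death is a PFS event on its own date. Protocol Table 14-5 carries the same footnote.
- SAP 4.6.1 says of censoring at treatment start: "This rule, however, only applies to the ‘PD component’ of the PFS or DOR assessment". It adds that a patient without a baseline assessment who dies within D2 of starting treatment "will be counted as having an event in the primary analysis of PFS".

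**The concern.** A patient with no BIRC data necessarily lacks a BIRC baseline, so both sets of rules cover that patient in the BIRC analysis. For an early death they disagree: one censors on day 1, the other counts an event at death. A programmer could code either and cite the SAP.

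Coding the unconditional sentence removes a death from an endpoint defined to include death from any cause, and the error can only raise the later BIRC PFS curve. It also reaches BIRC time to response. There, a non-responder with a PFS event is held in the risk set to maximum follow-up, while one without is censored at the last adequate assessment. For a patient with no assessment, that date is the start of treatment.

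**Working it through.** **Where the two rules differ**

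SAP 4.6.1 states that "the protocol defined schedule of tumor assessment is every 6 weeks" and uses a total window of 2 weeks.

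- D2 = 2 × 6 + 2 = 14 weeks (98 days). This reproduces the SAP's figure.
- Footnote a stops at the second scheduled assessment: 2 × 6 = 12 weeks.
- The protocol's imaging window is ±4 days (7.1 and 7.2.1.2), 8 days in total. That would give D2 = 84 + 8 = 92 days, or 13.1 weeks.

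For a patient with no BIRC data:

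| Status | Sentence in 2.8.1 | Table 2-1 and 4.6.1 |
|---|---|---|
| Alive, no event | Censored at start | Censored at start |
| Death by about 12 weeks | Censored at start | Event at death |
| Death between 12 and 14 weeks | Censored at start | Event under 4.6.1; censored under footnote a |
| Death after 14 weeks | Censored at start | Censored at start (situations A and C2; with no adequate assessment the reference date is treatment start) |

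Only the second and third rows conflict.

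**Size**

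Let k of N patients have no BIRC data and die inside the window. Assume no other early censoring. Let n be the number of the remaining N-k patients who are event-free at time t, after the last of those deaths.

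- Sentence in 2.8.1: S = n/(N-k)
- Deaths counted: S = n/N
- Ratio: N/(N-k)

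N is 100 and 60 for the pooled pre-treated and treatment-naïve MET mutant groups (SAP 2.2), and 27 is the planned size of Cohorts 5b and 7. The documents do not give k, so the values below are assumptions. The medians are phase I values from protocol 1.2.1.2.2 (7.39 and 3.55 months), also used as assumptions, with exponential times for the other patients.

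| N | k | Median (months) | n at 6 months | Sentence in 2.8.1 | Deaths counted | Ratio |
|---|---|---|---|---|---|---|
| 100 | 1 | 7.39 | 56 | 56/99 = 56.6% | 56.0% | 1.010 |
| 100 | 5 | 7.39 | 54 | 54/95 = 56.8% | 54.0% | 1.053 |
| 100 | 5 | 3.55 | 29 | 29/95 = 30.5% | 29.0% | 1.053 |
| 60 | 3 | 7.39 | 32 | 32/57 = 56.1% | 32/60 = 53.3% | 1.053 |
| 27 | 2 | 7.39 | 14 | 14/25 = 56.0% | 14/27 = 51.9% | 1.080 |

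In closed form, counting the deaths changes a median m to m × [1 + log2(1 - k/N)]. For m = 7.39 this gives 6.84 months with 5 of 100 or 3 of 60, and 6.57 months with 2 of 27.

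Over k from 1 to 5, N from 27 to 100 and both medians, the 6-month difference runs from 0.3 to 11 points. The top of that range needs 5 of 27 patients (18.5%) to be such deaths. With k = 0 there is no difference.

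**The case against.** The strongest reply is that the sentence only restates situation A's default, with the early-death exception still in force, since the preceding sentence refers to 4.6.1. That reading is possible, but the text does not say it. The same PFS text opens by censoring patients who have not progressed and are not known to have died, so the drafters wrote the condition there and left it out here.

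The second reply is that few patients can be affected, and this largely stands. Baseline imaging is mandatory before dosing (protocol 7.2.1 and Table 7-2), and baseline scans are submitted for BIRC review (protocol 4.1 and 7.2.1.3). A patient who dies in week 4 would normally have a BIRC-read baseline and so fall outside the sentence. SAP 2.7.1 and 2.7.3 also treat a lack of valid post-baseline assessments separately from having no BIRC data, which suggests the latter means nothing read at all. The term is undefined, so this is not certain.

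Three stronger readings are tempting, and the documents do not support them:

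- A reader might infer that the sentence is what removes every death among these patients. Deaths beyond about 14 weeks are already censored at treatment start under other rules. Censoring some deaths is also not an error in itself, because the protocol accepts it after two or more missing assessments.
- A reader might infer informative censoring, with the missing patients being those who deteriorate before imaging. Nothing in the documents shows this, and failed image transfer or reading is at least as consistent with the text.
- A reader might see a defect in the same patients counting as non-responders for ORR. ORR must classify every patient in the full analysis set, and PFS need not.

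**Conclusion.** Wrong as written, within a narrow scope. For a patient with no BIRC data who dies within about 12 to 14 weeks of first dose, the sentence contradicts the PFS definition, Table 2-1 footnote a and SAP 4.6.1 (the last two differ from each other between 12 and 14 weeks).

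Any bias is upward, by the factor N/(N-k) on later BIRC PFS. That inflation is conditional and should not be stated as fact: k is unknown, probably small and possibly zero. The percentages above rest on the assumed k and exponential times.

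BIRC PFS is a secondary, descriptive endpoint. Primary ORR, duration of response, overall survival and investigator-assessed PFS are untouched. The point merits correction because a written rule that can erase deaths is cheap to remove.

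**What to change.** Replace the sentence in SAP 2.8.1 with wording such as:

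> A patient with no BIRC-read assessment, at baseline or later, is censored for BIRC PFS on the first day of study drug, except that a death within D2 of that day is a PFS event on the date of death.

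Then:

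- Align Table 2-1 footnote a to the same window. The 12-week and 14-week limits cannot both stand, and the window inside D2 should be checked against the protocol's ±4 days.
- Report, by cohort and pooled group, how many patients have no BIRC data and how many of them died inside the window.

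BIRC time to response then follows from the corrected PFS event status. The cost is a sentence, a footnote, a small programming change and a line in a table. BIRC PFS may come out slightly less favourable.
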